Primary Endpoints	
1. TICI using NEWS Score [Time Frame: First treatment date up to discharge day (PI's discretion as per patients health condition)]
 
The median time in days from the start of treatment with the study drug / placebo to the persistent achievement of all of the following criteria:
 
 • Stopping a fever (which is defined as a decrease in axillary temperature below 37 ° C without the use of anti pyretic drugs); • Respiratory rate <22 /min; • Oxygen saturation (SPO2) > 95% when breathing in atmospheric air. Measured using pulse oximetry • Systolic blood pressure ≤200mmHg • Pulse rate 51-90beats/minute • Is conscious and alert 
[Note: Persistent achievement means the preservation of each of the criteria for at least 7days.]
 
2. TTIC using 7-point ordinal scale
 
3. Rate of progression to severe/critical COVID-19 disease based on NEWS score [Time frame: First treatment date up to 15days]
 
4. Rate of progression to severe/critical COVID-19 disease based on 7-point ordinal scale [Time frame: First treatment date up to 28days]
 
5. Time to COVID-19 nucleic acid testing negativity in oropharyngeal/nasal swab) [Time Frame: First treatment date up to 28days]

Secondary Endpoints	
 1. Incidence of ICU admissions [Time Frame: 28days] 2. Subject survival rate [Time Frame: 28days] 3. Incidence of mechanical ventilation due to COVID-19 infection [Time Frame: First treatment date up to 28days] 4. Change in clinical or laboratory assessment of comorbid condition [Time Frame: First treatment date up to 28days] 5. Percent of participants with worsening comorbid condition [Time Frame: First treatment date up to 28days] 6. Proportion of subjects in the treatment arm who had AE, SAE 7. Proportion of subjects in the placebo arm who had AE, SAE
Subject Selection Criteria	
Inclusion criteria
 
 1. 50 years or older

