Stopping the Study Drug	
 1. Completing 14 days of treatment 2. Progression to severe COVID-19: ViraCide will be stopped if subjects progresses to severe COVID-19 and require ICU admission, mechanical ventilation and any such situation where according to the PI the subject

	
cannot continue ViraCide. However, subject will be followed-up to capture data on ICU admission, incidence and mortality
 
 3. Progression of comorbid condition requiring admission to ICU or inability of the subject to take anything orally. However, subject will be followed-up to capture data on ICU admission, incidence and mortality 4. Subject's participation to the study is terminated 5. Study is terminated
Termination of Subject's Participation in the Study	
Any participant can be removed from the study:
 
 1. By his/her own free will to not continue in the study. Subject withdrawal of informed consent. 2. Loss of contact with the subject during the study. 3. Does not comply with dosing schedule (75%-125% non-compliance) 4. The development of AE / SAE requiring the withdrawal of the study drug. However all AE / SAE will be followed-up till the study duration 5. Pregnancy confirmed anytime during the study duration 6. Another reason, which, according to the PI, requires the termination of the subject's participation in the study.
Study Termination	
The study can be terminated if
 
 1. There is a major deviation in Protocol 2. Another reason, which, according to the PI, requires study termination

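### Subjects may be removed from the study, not only from study drug, for non-compliance, an adverse event or investigator opinion, with no provision to keep collecting efficacy outcomes

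*Protocol*

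**What the plan says.** The protocol synopsis has two separate entries, one for stopping study drug and one for leaving the study. The second opens with "Any participant can be removed from the study" and lists six grounds. Grounds 1 and 2 are withdrawal of consent and loss of contact. Ground 3 is "Does not comply with dosing schedule (75%-125% non-compliance" (the bracket closes there). Ground 4 is "The development of AE / SAE requiring the withdrawal of the study drug", followed by "However all AE / SAE will be followed-up till the study duration". Ground 5 is pregnancy. Ground 6 is open-ended: "Another reason, which, according to the PI, requires the termination of the subject's participation in the study".

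Under Stopping the Study Drug, items 2 and 3 (progression of COVID-19 or of a comorbid condition) carry the promise that the "subject will be followed-up to capture data on ICU admission, incidence and mortality". No such promise appears under the termination entry. Stopping item 4 links the two entries: drug stops when participation is terminated.

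Primary endpoint 4 is "Rate of progression to severe/critical COVID-19 disease based on 7-point ordinal scale [Time frame: First treatment date up to 28days" (the bracket closes there). PCR negativity, ICU admission, survival, ventilation and the comorbidity endpoints are also given a 28-day horizon. In the SAP, section 3 places efficacy in the PP set (all visits completed) and the mITT set (at least one dose and one completed visit). Sections 5.2 and 5.3 name the tests but give no rule for missing outcomes.

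**The concern.** Removal for an adverse event or poor intake can depend on tolerability and on how ill the subject is, and so on treatment arm. If outcome collection ends with removal, the missing outcomes may not be a random sample, and the analysed subjects are no longer the groups that were randomized. At stake are PCR negativity, time to clinical improvement, progression and the comorbidity outcomes. The 10% dropout allowance replaces numbers; it does nothing about bias.

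The trigger for ground 3 is also unclear. The stated range could be the acceptable intake or the range that triggers removal, so sites could apply it differently.

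**Working it through.** **1. The plan's own figure.** The protocol's Statistical Analysis entry asks for 112 completed cases (56 per arm) and, with 10% dropout, enrols 124 (62 per arm). 112 × 1.10 = 123.2, rounded up to 124, so the figure reproduces. (Dividing instead, 112 / 0.90 = 124.4, which rounds up to 125.) The 112 cannot be rederived because no effect size is stated. 10% of 62 is 6.2, so about 6 per arm may lack outcomes, leaving 56.

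**2. What follow-up is stated after each event.**

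| Event | Leaves study? | Follow-up stated |
|---|---|---|
| Drug stopped for COVID-19 or comorbidity progression | No | ICU admission and mortality |
| Non-compliance (ground 3) | Can be removed | None |
| AE/SAE requiring drug withdrawal (ground 4) | Can be removed | AE/SAE only |
| Pregnancy (ground 5) | Can be removed | None |
| Investigator opinion (ground 6) | Can be removed | None |

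**3. What can be lost.** In the protocol's laboratory schedule, Days 1 and 7 have no labs, and Day 15 (or discharge, if earlier) has the only post-baseline swab. The SAP lists a secondary PCR endpoint at Days 1, 7 and 15, but the protocol schedules no swab on Days 1 or 7. Compliance is checked at Days 7 and 15. A subject removed at Day 7 would have no scheduled post-baseline swab and may be unable to show the 7 days of persistence that clinical improvement requires. Such a subject drops out of PP. In mITT the subject is counted in the set, but nothing says how the absent outcome is handled.

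**4. Illustration.** Assumptions, none from the documents: 6 of 62 removed in each arm, and 6 true progressors in each arm (6/62 = 9.7%), so the true difference is 0.
- ViraCide loses 3 progressors among its 6 removals: (6 − 3)/(62 − 6) = 3/56 = 5.4%.
- Placebo loses none: 6/56 = 10.7%.
- Spurious difference: 3/56 = 5.4 percentage points.
- If both arms lose 3: 3/56 against 3/56, difference 0.

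**5. Bounds that need no event rate.** With m of 62 outcomes missing, an arm's rate can lie anywhere in an interval of width m/62, and the arm difference in one of width 2m/62.
- m = 3: 6/62 = 9.7 points.
- m = 6: 12/62 = 19.4 points.
- m = 12: 24/62 = 38.7 points.

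**6. When bias arises.** Let p be the true risk, r the removed fraction and q the risk among those removed. The completers' risk is (p − rq)/(1 − r). The table assumes p = 20% in both arms. The two-sided type I error of the chi-square test comes from 200,000 simulated trials per row, with 62 per arm and completers analysed.

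| Removed (ViraCide / placebo) | Risk in removed (ViraCide / placebo) | Bias, points | Type I error |
|---|---|---|---|
| 10% / 10% | 50% / 50% | 0 | 5.1% |
| 10% / 10% | 50% / 20% | −3.3 | 7.4% |
| 15% / 5% | 50% / 50% | −3.7 | 8.1% |
| 15% / 5% | 50% / 20% | −5.3 | 11.3% |
| 10% / 10% | 80% / 20% | −6.7 | 15.7% |

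Row 2, for example: (0.20 − 0.10 × 0.50)/0.90 = 16.7% against 20.0%. Removal must be related to outcome and must also differ between arms, either in its frequency or in who is removed.

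**The case against.** The strongest reply is that the wording is permissive. Subjects can be removed, and no sentence says that efficacy assessments stop. That stands: a reader might infer that outcomes are certainly lost, and the documents do not say so. What they show is that nothing requires collection to continue, although the authors wrote such a requirement where they wanted one.

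Several limits on scope also stand:
- For AE removals, deaths, ICU admissions and ventilation may still surface through AE/SAE follow-up.
- Subjects whose drug is stopped for progression keep ICU and mortality follow-up, so the gap mainly concerns those removed before progressing.
- Removal at the Day 15 compliance check would forgo only the Day 28 call.
- Pregnancy is a minor route in subjects aged 50 or older with a negative test at entry.

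The illustration is demanding. It needs half of the removed ViraCide subjects to be progressors, against 9.7% overall, and it attributes the whole dropout allowance to removals, although consent withdrawal and loss of contact also contribute. It shows how the bias works and does not forecast its size.

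It is tempting to say that the Day 28 call could recover most of what is missing. As listed, it covers PCR negativity, COVID-19 mortality, symptoms, comorbidity and adverse events. It does not cover NEWS, the 7-point scale, ICU admission or ventilation.

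**Conclusion.** The point holds as a weakness worth correcting. The plan permits removal from the study on four grounds other than consent withdrawal and loss of contact. It does not provide for efficacy outcomes afterwards, and the SAP is silent on missing outcomes. The loss is most likely for PCR negativity, clinical improvement, NEWS or ordinal progression and comorbidity outcomes.

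A reader might infer that the trial is biased towards ViraCide. The documents do not support that: equal, or equally outcome-related, removal in the two arms gives no bias under the null, and differential removal could act in either direction. The 5.4-point figure and the simulated error rates rest on assumed event rates and removal patterns. The 19.4-point bound rests only on 6 missing outcomes per arm.

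The range in ground 3 is ambiguous. The documents do not settle which reading is meant, and the wording must be reconciled.

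**What to change.** Leave what happens to study drug under each ground exactly as it now is, including the link through stopping item 4. Add to the termination entry that, for grounds 3 to 6, ending treatment does not end outcome collection. Unless consent is withdrawn or contact is lost, the remaining scheduled Day 7 and Day 15 assessments and the Day 28 call are completed.

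Add ICU admission, mechanical ventilation and 7-point ordinal status to the Day 28 call. State in SAP section 3 that data collected after removal are used in the mITT analysis, and in sections 5.2 and 5.3 how outcomes still missing are handled. Best/worst-case bounds of the kind shown above would be a simple sensitivity analysis. Separately, have the sponsor reconcile the compliance range in ground 3.

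The cost is wording, plus a few extra assessments and contacts for removed subjects at times already scheduled, including the Day 15 swab, bloods and ECG. The sample size does not change. If outcomes are obtained for every removed subject, the part of the bounds due to removal shrinks to zero; losses from consent withdrawal and lost contact remain.

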Study Population	
 • 50 years or older • Positive RT- PCR for Sars-Co-V2. • Either asymptomatic or have mild symptoms. Onset of symptoms within no more than 4days • With chronic stable medical conditions: Diabetes Mellitus, or Hypertension, or chronic heart disease.
Study Duration	Total study duration approximately 35 days Screening: 04 days Treatment duration: 14 days Follow-up: 14 days from end of treatment

Number of Sites	02 (two)
Treatment Duration	14 days
Treatment Arms	
Two treatment arms
 
 • Arm A: ViraCide softgels: 3 soft gels, two times every day after breakfast and dinner for 14 days+ SOC Therapy • Arm B: Placebo softgels: 3 soft gels, two times everyday after breakfast and dinner for 14 days + SOC Therapy
Purpose of the study	To study the effectiveness and safety of the Study Drug, ViraCide
	softgels by oral administration compared with placebo softgels in 50 years or older subjects with asymptomatic or mildly symptomatic coronavirus infection (COVID-19) and stable comorbidities.
Objectives	
Primary Objectives
 
1. To evaluate the efficacy of “ViraCide” in the management of mild COVID-19 disease
 
Secondary Objectives
 
1. To evaluate the safety of “ViraCide” in the management of mild COVID-19 disease

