Visits of Assessment	
Screening and 3 visits and one telephonic follow-up
 
Screening Inclusion/Exclusion Criteria, Subject Inform Consent, Demography, Medical History, Physical Examination, Vital Signs, HIV; HBsAg; HCV; Hs-CRP; Pulse oximetry; NEWS scoring; 7- point ordinal scoring; Medication list review (medications being taken for comorbid conditions), Lab assessment; Urine analysis Note: Patients who do not meet the study inclusion exclusion criteria during screening should not be randomized into the study.
 
Day 1 Randomization, Vital Signs, Pulse oximetry, AE/SAE, Concomitant Medication, ViraCide/ Placebo treatment start, NEWS scoring; 7-point ordinal scoring
 
Day 7 Physical Examination, Vital Signs, AE/SAE, Concomitant Medication, ViraCide/ Placebo Compliance check, Pulse oximetry; NEWS scoring; 7-point ordinal scoring. (Note: If the subject is discharged on this day as per PI's discretion and patient's health condition then assessment scheduled for day 15 will be carried out on discharge day).
 
Day 15 Physical Examination, Vital Signs, AE/SAE, Concomitant Medication, ViraCide/ Placebo treatment end, RT-PCR for

	
Sars- Co-V2, Hs-CRP, Safety Lab Tests, Pulse oximetry; NEWS scoring; 7-point ordinal scoring, ViraCide/ Placebo Compliance check, Lab assessment including urine analysis
 
Day 28 Phone call follow up for time :
 
 • until negative RT-PCR for Sars-Co- V2, COVID-19 related mortality, • development of any COVID-19 symptom, • development of any worsening of comorbid condition; • Development of new AE/SAE; Resolution status of previous AE/SAEs 
Note: If subject is discharged before Day 15 on PI's discretion as per patients health condition, then assessments scheduled for Day 15 will be carried out on the discharge day (as far as possible and those not performed will be noted on appropriate CRF page) and Day 15 visit will be done telephonically.

Laboratory Investigations	
Screening: Recording RT-PCR- Sars-Co-V2 result; Urine pregnancy test; HIV; HBsAg; HCV; Hs-CRP; Hematology* + Biochemistry + Urine analysis*; ECG
 
Day 1: No labs
 
Day 7: No labs
 
Day 15: Oropharyngeal/nasal swab for PCR- Sars-Co-V2; Hematology* + Biochemistry + Urine analysis*; ECG; Serological biomarker: Hs-CRP

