5. Time to COVID-19 nucleic acid testing negativity in oropharyngeal/nasal swab) [Time Frame: First treatment date up to 28 days]

Confidential & Proprietary

The unauthorized use, disclosure, distribution or copying of these information is strictly prohibited

Secondary Efficacy Endpoints:

1. Incidence of ICU admissions [Time Frame: 28 days]
2. Subject survival rate [Time Frame: 28 days]
3. Incidence of mechanical ventilation [Time Frame: First treatment date up to 28 days]
4. Time to COVID-19 nucleic acid testing negativity in oropharyngeal/nasal swab) [Time Frame: Days 1, 7, 15]
5. Change in clinical or laboratory assessment of comorbid condition [Time Frame: First treatment date up to 28 days]
6. Percent of participants with worsening comorbid condition [Time Frame: First treatment date up to 28 days]

Safety Endpoints

1. Proportion of subjects in the treatment arm who had AE, SAE
2. Proportion of subjects in the placebo arm who had AE, SAE

Confidential & Proprietary

Any unauthorized use, disclosure, distribution or copying of these information is strictly prohibited

3 Analysis sets

Per protocol subset (PP)

Subjects without any Major protocol violation would be included in the per-protocol population, including those subjects who have completed all the visits, who did not take any prohibited medications during the study period and whose CRF was completed as requested.

Modified Intention to treat subset (mITT)

The term “mITT” includes all randomized subjects who met all inclusion/exclusion criteria, administered at least one dose of assigned product with at least completed one visit will be included in the mITT population.

Safety analysis subset

The safety population will consist of all subjects enrolled in the study, who have received at least one dose of study products i.e. mITT population.

Methods of Analysis

Primary Efficacy and secondary endpoints will be analyzed using the PP & mITT population. And Safety variables as per mITT only.

4 Data Handling

Data entry into CRF must be performed as per general CRF data entry guidelines, summarized at the time of data entry feasibility training. Data entry will be made as per source document without interpretation or modification to maintain consistency and accuracy of the data. Study specific

Confidential & Proprietary

Any unauthorized use, disclosure, distribution or copying of these information is strictly prohibited

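### Termination item 3 of the protocol gives a dosing non-compliance threshold that cannot be applied as written

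*Protocol*

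**What the plan says.** The protocol synopsis, under Termination of Subject's Participation in the Study, opens with "Any participant can be removed from the study" and then lists six grounds. Item 3 is "Does not comply with dosing schedule (75%-125% non-compliance". It does not say what the percentage is a percentage of, or over what period.

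The regimen is under Treatment Arms: "ViraCide softgels: 3 soft gels, two times every day after breakfast and dinner for 14 days", with the same schedule for placebo. Under Visits of Assessment, compliance is checked on Day 7 ("Concomitant Medication, ViraCide/ Placebo Compliance check, Pulse oximetry") and again on Day 15. Neither visit gives a limit.

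The SAP's section 3 defines the per-protocol set by absence of major violations, completion of all visits, no prohibited medication and a completed CRF. It defines the mITT set by eligibility, at least one dose and at least one completed visit. Neither definition contains an intake limit. The same section says "Primary Efficacy and secondary endpoints will be analyzed using the PP & mITT population".

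**The concern.** A range centred on 100% of planned intake normally describes acceptable adherence. Here it carries the opposite label. Taken at its word, the parenthesis marks people who took their softgels as non-compliant and passes people who took few or none.

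At stake is a rule for removing subjects from a two-site trial. The sites need to apply it in the same way, and neither document offers other wording to fall back on. Item 3 also has no follow-up provision of its own, whereas item 4 (AE/SAE) and items 2 and 3 of Stopping the Study Drug do.

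**Working it through.** **Inputs**

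- Softgels per dose: 3; doses per day: 2; days: 14 (Protocol, Treatment Arms).
- Range: 75% to 125%, labelled non-compliance (Protocol, Termination item 3).

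The range is a stated limit, not a calculated result, so there is no figure of the plan's to reproduce. The check is whether any reading gives a workable rule.

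**Conversion to softgels**

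- Full course: 3 × 2 × 14 = 84.
- Lower limit: 0.75 × 84 = 63.
- Upper limit: 1.25 × 84 = 105.

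**Reading A: the percentage is intake.** Non-compliant means 63 ≤ taken ≤ 105.

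**Reading B: the percentage is doses missed.** Non-compliant means missed ≥ 63, so taken ≤ 84 − 63 = 21. The upper limit would be 105 missed out of 84, which cannot happen.

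**Reading C: the percentage is absolute deviation from plan.** Non-compliant means 63 ≤ |taken − 84| ≤ 105. That is taken ≤ 21, or taken from 84 + 63 = 147 to 84 + 105 = 189.

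**Reading D: the probable intent.** Non-compliant means taken < 63 or taken > 105.

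| Softgels taken | % of 84 | A | B | C | D |
|---|---|---|---|---|---|
| 0 | 0 | not flagged | flagged | flagged | flagged |
| 21 | 25.0 | not flagged | flagged | flagged | flagged |
| 42 | 50.0 | not flagged | not flagged | not flagged | flagged |
| 62 | 73.8 | not flagged | not flagged | not flagged | flagged |
| 63 | 75.0 | flagged | not flagged | not flagged | not flagged |
| 84 | 100.0 | flagged | not flagged | not flagged | not flagged |
| 105 | 125.0 | flagged | not flagged | not flagged | not flagged |
| 106 | 126.2 | not flagged | not flagged | not flagged | flagged |
| 120 | 142.9 | not flagged | not flagged | not flagged | flagged |

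Reading A flags full adherence and passes a subject who took nothing. Readings B and C both pass a subject who took half the course and one who took 143% of it. Only D gives a sensible two-sided rule around 100%, and D is not what the text says.

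**The case against.** The strongest reply is that the operative words of item 3 are failure to follow the dosing schedule, and the percentage is only a gloss. A subject who took 84 of 84 followed the schedule, so the leading clause does not reach them. Most sites would probably apply the item as outside 75% to 125% without being told. Removal is discretionary, and item 6 lets the investigator end participation for another reason, so a subject with very low intake is not out of reach. All of this stands, and it limits the practical harm. It does not rescue the parenthesis, which is the only number sites are given and which they must reverse before using.

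It is also fair that the intended rule is an inference. Neither document calls 75% to 125% an acceptable window, and the public protocol text is a synopsis.

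Two stronger readings are tempting, and the documents support neither.

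- *Adherent subjects will be removed.* A reader might infer this from reading A. It needs the parenthesis to override the leading clause and the permissive wording to be treated as mandatory.
- *The rule removes subjects, or drops them from the per-protocol set, because they progressed.* The argument is that drug is stopped on progression ("ViraCide will be stopped if subjects progresses to severe COVID-19 and require ICU admission"), so such subjects fall short of 84, while "Rate of progression to severe/critical COVID-19 disease based on NEWS score" is a primary endpoint. But neither document fixes 84 as the denominator or sets an intake limit for the per-protocol set. A subject whose drug was stopped as the protocol directs has followed it, and follow-up is expressly retained. The next stopping rule, "Progression of comorbid condition requiring admission to ICU or inability of the subject to take anything orally", concerns comorbidity or oral intake, not the COVID-19 progression counted in primary endpoints 3 and 4. This would be a fault in a badly drafted correction, not in the current text.

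**Conclusion.** Wrong as written, with minor impact. The one numeric compliance threshold in the two documents is unworkable under each of the three literal readings tried. The error is in the definition: no sample size, power or type I error figure depends on it, and mITT and safety-set membership do not use it.

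Confidence is high that the wording is defective. It is lower on what was meant. That intake below 63 or above 105 of 84 softgels is the intended ground for removal rests on two things: the range is symmetric about 100%, and the literal readings fail. The sponsor should confirm it. The conclusion also assumes that no fuller compliance wording exists outside the published text.

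**What to change.** Replace the parenthesis in Termination item 3, once the sponsor has confirmed the intent, with:

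> softgels taken <75% or >125% of those scheduled up to the compliance check or, if earlier, the date study drug was stopped under the protocol for any reason (progression, comorbid condition, or AE/SAE).

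The denominator is there so that the corrected rule works at both checks. By Day 7 a fully adherent subject has been scheduled 6 × 6 = 36 softgels (Days 1 to 6) or 6 × 7 = 42 (Days 1 to 7), which is 43% or 50% of 84. Measured against the amount scheduled to date, that subject is at 100%. The stop date should cover AE-driven withdrawal as well as the progression and comorbidity stopping rules, so that stopping drug as directed is never counted as non-compliance.

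The cost is one protocol sentence, with no new visit or assessment. The stop date has to be used when the percentage is calculated. No SAP change is required.

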CLINICAL STUDY PROTOCOL

PROTOCOL TITLE

**A DOUBLE BLIND, RANDOMIZED, PLACEBO CONTROLLED STUDY
TO EVALUATE EFFICACY AND SAFETY OF “VIRACIDE”
IN THE MANAGEMENT OF CORONA VIRUS DISEASE 2019 (COVID-19)**

**Protocol Number: NS-VC-CT01-20
Clinicaltrial.gov ID: NCT04596085**

STUDY SYNOPSIS

Title	A double blind, randomized, placebo controlled study to evaluate efficacy and safety of “ViraCide” in the management of corona virus disease 2019 (COVID-19).
Study Description	
This is a double blind randomized placebo controlled study will be conducted on 124 subjects, 50 years and older with mild or asymptomatic COVID-19. If symptomatic, symptoms are mild (cough, weakness, sore throat, low grade fever 38.50C, respiratory rate should not be more than 22 / min, resting SpO2 >95%, normal highly sensitive C-reactive protein (HS-CRP) (<10mg/L). There are no signs of dehydration, sepsis or shortness of breath.
 
The study will be conducted at two centers. There will be a screening visit at Day -4 followed by three visits at the center at Days 1, 7 and 15 and a follow-up visit on Day 28. All participants will be randomized to receive either ViraCide (investigational product) or matching placebo. All subjects will receive SOC therapy.
 
Note: If subject is discharged before Day 15 PI’s discretion as per patients health condition, then assessments scheduled for Day 15 will be carried out on the discharge day (as far as possible and those not performed will be noted on appropriate CRF page) and Day 15 visit will be done telephonically.

Investigational Product/Study drug	ViraCide softgels given per orally
Comparison product	Matching placebo of ViraCide softgels given per orally
Study Design	Double blind, randomized, placebo controlled study. Subjects will be randomized to the experimental and control groups in a 1:1 ratio. In each group 62 subjects will be recruited, a total of 124 subjects. Subjects of the experimental arm will receive treatment with Study Drug, ViraCide and SOC. The control group will receive matching placebo and SOC. The study consists of the stages of screening, therapy, observation. There will be no switching of subjects between the arms. Participants will receive Study drug or matching placebo for 14 days during the study.
Sample Size	124, including 10% dropouts

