	
 2. Both male and female subjects will be included 3. Positive oropharyngeal/nasal swab RT-PCR for Sars-Co- V2. Diagnosed not more than 2 days ago (diagnosis ≤ 2 days). 4. Either asymptomatic or have mild symptoms. Onset of symptoms within no more than 4 days. If symptomatic, symptoms are mild (cough, weakness, sore throat, low grade fever 38.50°C, respiratory rate should not be more than 22 / min, resting SpO₂ $>95\%$, normal highly sensitive C-reactive protein (HS-CRP) ($<10\text{mg/L}$). There are no signs of dehydration, sepsis or shortness of breath. 5. Chronic stable medical conditions: diabetes mellitus, or hypertension, or chronic heart disease. Under treatment and controlled by medication 6. Signed informed consent/or consent given through text message, WhatsApp or e-mail. 7. Ability to understand the requirements of the Research Protocol and follow the research procedures. 8. Subject should be willing to be managed in isolation wards 9. Negative pregnancy test (for female participants) 10. Adequate contraception for study duration 
Exclusion criteria
 
 1. Less than 50 years 2. With severe COVID-19 symptoms requiring immediate hospitalization 3. Investigator considers the subject unsuitable for ViraCide 4. History of symptoms of more than 4 days 5. COVID-19 diagnosed >2 days ago using oropharyngeal/nasal swab RT-PCR for Sars-Co-V2 6. History of cardiopulmonary resuscitation

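### Entry limits are reviewed only at screening, and no rule applies the Day 1 measurements before randomisation, so a subject may be randomised after leaving the mild, early-disease range

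*Protocol*

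**What the plan says.** **Timing.** The protocol synopsis (Study Description) states: "There will be a screening visit at Day -4 followed by three visits at the center at Days 1, 7 and 15". Under Study Duration it gives "Screening: 04 days".

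**Early-disease limits.** Inclusion criterion 3 requires a positive PCR: "Diagnosed not more than 2 days ago (diagnosis ≤ 2 days". Inclusion criterion 4 asks for "Onset of symptoms within no more than 4 days", and exclusion criterion 4 removes subjects with a "History of symptoms of more than 4 days". None of these names the date to which the days are counted. Exclusion criterion 20, by contrast, dates its 30-day limit from screening.

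**Mild-disease limits.** For symptomatic subjects, inclusion criterion 4 also sets a temperature limit, "respiratory rate should not be more than 22 / min", resting SpO2 above 95%, hs-CRP below 10 mg/L, and no dehydration, sepsis or shortness of breath.

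**When the criteria are applied.** Under Visits of Assessment, the inclusion/exclusion review is listed at Screening and at no other visit. The note there says: "Patients who do not meet the study inclusion exclusion criteria during screening should not be randomized into the study". The Day 1 entry begins: "Randomization, Vital Signs, Pulse oximetry, AE/SAE, Concomitant Medication, ViraCide/ Placebo treatment start", followed by NEWS and the 7-point score. It lists no eligibility review and no physical examination. Laboratory Investigations schedules no tests on Day 1.

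**Analysis.** SAP section 3 limits the mITT set to randomised subjects who met all criteria, without saying at what time, and describes the safety population as that same set.

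**The concern.** The trial is meant to study early, mild or asymptomatic infection in people aged 50 or older with stable comorbidity. In an acute infection a few days matter. A screening interval as long as the whole symptom limit, and twice the diagnosis limit, can undo the restriction that those limits were written to impose. If nothing ties Day 1 findings to eligibility, a subject who passed screening may be randomised when no longer within the mild range.

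Three things are at stake.

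- **Population description.** A report that subjects had at most 4 days of symptoms and at most 2 days since diagnosis might not be true at first dose.
- **Baseline spread.** Time since onset would vary more than intended. The between-group tests in SAP section 5.2 are Mann-Whitney, chi-square and t-tests, with no adjustment for it.
- **Progression endpoints.** Primary endpoints 3 and 4 count progression from the first treatment date. A subject already deteriorating on Day 1 can contribute an event to them that began before treatment.

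There is also a loose end in the analysis sets. Because the mITT definition gives no time point, it is unclear whether a dosed subject who was inside the limits at screening and outside them on Day 1 belongs in the efficacy and safety analyses. That should not be left to be decided after randomisation.

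**Working it through.** The documents give no figure for time since onset or diagnosis at first dose, so there is none to reproduce on this point. The only calculated number is the enrolled total: 112 × 1.10 = 123.2, rounded up to 124 (division, 112 / 0.90 = 124.4, would round up to 125). Nothing below depends on it.

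**Inputs, all from the protocol synopsis**

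- Symptom limit: 4 days (inclusion 4, exclusion 4).
- Diagnosis limit: 2 days (inclusion 3).
- Interval from a Day -4 visit to Day 1: 4 days if the count runs -4, -3, -2, -1, 1; 5 days if a Day 0 is counted. It is shorter if screening takes place later in the 4-day period.

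**Formula.** If a limit L is tested only at screening and the interval to first dose is g days, the maximum at first dose is L + g.

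| Interval g (days) | Maximum symptom duration (4 + g) | Maximum time since diagnosis (2 + g) | Minimum time since diagnosis (0 + g) |
|---|---|---|---|
| 0 | 4 | 2 | 0 |
| 1 | 5 | 3 | 1 |
| 2 | 6 | 4 | 2 |
| 3 | 7 | 5 | 3 |
| 4 | 8 | 6 | 4 |
| 5 (Day 0 counted) | 9 | 7 | 5 |

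The last column follows because the PCR result is recorded at screening, so diagnosis cannot be later than that visit. At g = 3 or more even the most recent diagnosis exceeds 2 days. Counting the 2-day limit to randomisation would therefore exclude everyone screened at Day -4.

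For subjects already symptomatic at screening, symptom duration at g = 4 lies between 4 and 8 days. Only those whose symptoms began on the screening day would still be inside the limit. Subjects without symptoms have no symptom clock.

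**Mild-disease limits, screening against Day 1**

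- Temperature, respiratory rate and SpO2 are components of the NEWS-based criteria in primary endpoint 1. The Day 1 vital signs, oximetry and NEWS score should supply them again.
- hs-CRP is not repeated, as Day 1 has no laboratory tests.
- Shortness of breath, dehydration and sepsis are not named as Day 1 assessments.
- No sentence says that Day 1 values must still satisfy inclusion criterion 4, or that they must be read before randomisation.

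So the Day 1 measurements largely exist. What is missing is the rule that uses them.

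**The case against.** The strongest reply is that the protocol nowhere orders the randomisation of an ineligible subject. The note bars those who fail during screening; it does not say that everyone who passes must be randomised. Screening is also described as a 4-day period, so the words could be read as running up to randomisation. Several exclusions carry no date: severe symptoms requiring hospitalisation, respiratory failure, and the investigator's view that the subject is unsuitable. An attentive site would probably use them for a subject who was plainly worse on Day 1. The Day 1 NEWS and 7-point scores would also make such worsening visible in the baseline data.

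Much of this stands. A reader might infer that out-of-range subjects will certainly be randomised. The documents do not support that: the limits have no stated reference date, the interval may be shorter than 4 days, and with no interval nobody exceeds either limit. A reader might also infer that the mild-disease measurements are not repeated on Day 1; apart from hs-CRP and the signs noted above, they are.

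Nor do subjects whose symptoms resolve between screening and Day 1 fall outside the population. Asymptomatic infection is eligible, so they would pass a clinical re-check, and no such check would detect viral clearance.

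The objection does not remove the gap. The only listed eligibility review is at screening, the undated exclusions say nothing about elapsed time, and a moderate change, such as SpO2 no longer above 95%, need not trigger any of them. A visible baseline value does not help if the planned chi-square comparison of progression makes no use of it.

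**Conclusion.** The point holds as a gap in the eligibility procedure. A subject treated in full compliance with the protocol may be randomised after leaving the mild range. The same subject may receive the first dose with up to 8 days of symptoms against a limit of 4, and up to 6 days since diagnosis against a limit of 2 (9 and 7 if a Day 0 is counted). These are maxima. They assume that screening takes place at Day -4 and that the limits are tested there only. The documents do not allow an estimate of how many subjects would be affected.

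The effect is on the population description, on baseline spread, and on worsening before treatment that enters primary endpoints 3 and 4. A reader might go further and infer bias between the arms or a loss of planned power. The documents support neither. Allocation is randomised and blinded, and nothing suggests that the interval would differ by arm. No sample-size or power figure changes.

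**What to change.** **Day 1 check.** Before randomisation, confirm from the measurements already scheduled that the subject still meets the existing clinical limits of inclusion criterion 4, and do not randomise those who do not. hs-CRP is excepted because Day 1 has no laboratory tests. For shortness of breath, dehydration and sepsis, the investigator's confirmation can go on the same CRF line. This sets no new threshold and adds no laboratory test. It costs one CRF check and some extra screen failures.

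**Reference dates.** Separately, the sponsor should reconcile the 4-day symptom limit and the 2-day diagnosis limit with the 4-day screening period by stating the date to which each is counted. This is not only a matter of wording: counting the 2-day limit to randomisation is incompatible with screening at Day -4 unless the screening window is shortened. If the limits are counted to screening, the population should be described that way in the protocol and the report.

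**SAP.** The mITT definition in section 3 should refer to the same time point, so that membership is settled before randomisation.
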